We will exclude clients who are in need of detoxification, are at acute risk of suicide or homicide, fail a capacity-to consent questionnaire, are cognitively impaired (as detected on the Mini-Cog Examination) and self-report contraindications to participating in a weight loss program, including: receiving active cancer treatment (radiation/ chemotherapy), have liver failure, have been told by a doctor that they had anorexia, had a cardiovascular event (e.g., unstable angina, myocardial infarction) within the past 6- months, ever had or planning to have weight loss surgery in the next 18-months, unable to walk, and (for female participants) currently pregnant or planning a pregnancy during the study period. Individuals who are 65 years or older will also be screened for cognitive impairments using the MiniCog examination (see a description of the Mini-Cog examination in the informed consent process section below). Those that fail the mini-cog will be excluded from the study because of possible cognitive impairment issues.

At the baseline assessment (and also at 6, 12, and 18-month), participants complete the BASIS-24 questionnaire which includes questions regarding potential psychiatric symptoms. If participants

indicate anything other than “never” to questions regarding “how often did you think about ending your life” and “how often did you think about hurting yourself”, clients are taken for immediate in-person evaluation and counseling by a member of their treatment staff. A member of the treatment team is always on-site and researchers will accompany the participant to the treatment team’s offices and a case manager (or other provider) will then conduct a formal assessment regarding their risk, per agency’s protocols. No specific referral form will be used as participants are already receiving support services from the agency. A member of the treatment services team (e.g., case manager) will formally evaluate the participant, directly provide counseling, and make referrals to an appropriate treatment setting as necessary (e.g., emergency room, psychiatrist). Enrollment into the study will only proceed if the agency determines that the participant is not at acute risk of suicide. The supportive housing agencies directly provide extensive mental health treatment support and have close linkages to local hospitals, detox facilities, and other treatment settings to which participants can be routinely referred as needed.

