[name], study Principal Investigator, is a certified GLB group-facilitator having completed the 2- day facilitator training workshop provided by the DPSC and having facilitated GLB groups in previous studies. This training also provides ongoing implementation support through telephone conferences calls, on-line discussion board, GLB-listserv, GLB program directory, and Newsletters.

Description of Peer Specialists

Peer GLB will be facilitated by trained peer-specialists employed at the supportive housing agencies. According to SAMHSA, a peer specialist "is a person who uses his or her lived experiences of recovery from mental illness and/or addiction, plus skills learned in formal training, to deliver services in behavioral health [and other] settings to promote mind-body recovery and resiliency." The Peer Specialists will be employees hired by the supportive housing agency. They are individuals who are 18 and over, who have at least a high school education or GED equivalent, and who have completed prior training enabling them to become service providers. The qualifications of peer specialists hired at each study site include prior completion of extensive training in delivering services to populations with serious mental illness as well as certification, or in the process of receiving certification, for the delivery of peer specialist services per state regulations. These trainings to become a peer specialist include developing an understanding of the public mental health system, becoming integrated into the workforce, and intensive training in how to assist people with SMI in their recovery. As a result of these completed trainings, the peer specialists have expertise in 1) sharing their personal recovery experience to help others understand their experience of mental illness and treatment services, 2) assisting persons with SMI to identify

and overcome barriers to recovery and participation in services, and 3) assisting persons with SMI to develop skills that promote recovery, health, and wellness. Through the completion of this training and previous experience, peer specialists will have the ability to provide services either one-on-one or in groups. Each supportive housing agency will also provide peer specialists with its usual orientation and training that is required of all new employees prior to delivering services to clients.

Peer Specialist Intervention Training and Supervision

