Lastly, participants assigned to the intervention will be asked to complete one semi-structured qualitative interview that focuses on the participants' experiences with the group facilitator and explores specifically how intervention services were delivered from the participants' perspective. This semi-structured qualitative interview will be conducted after the transition phase of an intervention group has been completed. Participants who attended at least two intervention sessions will be asked to complete the interview and a total of 55 participants are expected to participate. The interviews last approximately 90 minutes and will be conducted in person by Drs. [name] (PI) & [name] (PD) and/or a trained research assistant at the study site. Examples of questions include: Is there anything that makes the healthy lifestyle peer specialist/facilitator unique from other provider staff that you have worked with? What are some of the peer specialist's/facilitator's best qualities? What kinds of things did your peer specialist/facilitator do to model or show you how to engage in a healthy lifestyle?

Criteria for Early Discontinuation

Early discontinuation from the study will be ascertained by the group facilitator in consultation with the participants' service providers (e.g., case managers) at the supportive housing agency. Participants who during the course of the project are in need of detoxification and are at acute risk of suicide or homicide will be referred for treatment and discontinued from the study. Moreover, participants that develop contraindications to participating in a weight loss program, such as receiving active cancer treatment (radiation/chemotherapy), develop liver failure, have a cardiovascular event (e.g., unstable angina, myocardial infarction) and become pregnant or are planning a pregnancy during the study period will be discontinued from the study.

4. Study Drugs or Devices: Not applicable.

5. Study Instruments

Structured Interviews: Baseline and 6, 12, and 18-month Follow-Up

The structured interview includes the collection of basic anthropometric measures and a simple physical activity measure by trained research staff:

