The structured interview will also include a series of standardized instruments to collect information about client's demographics, self-reported mental and physical health conditions, and use of medical and mental health services in the past 12-months. We will also use the following standardized instruments: Self-Efficacy Exercise Scale and the Weight Efficacy Lifestyle (WEL) questionnaire to measure participants' levels of self-efficacy for engaging in physical activities and a healthy lifestyle behaviors, the International Physical Activity Questionnaire (IPAQ): Short Form to measure participants engagement in physical activity during the past seven days, the BASIS-24 to measure mental health symptoms, the Recovery Assessment Scale to measure the different aspects of recovery the SF-12 to measures participant health and mental health-related quality of life, the Perceptions of Food Environment Scale to measure the availability of health and unhealthy options in their neighborhood, the Client Satisfaction Questionnaire (CSQ) to measure participants satisfaction with our health lifestyle program (administered only at the 6 & 12-month follow-up), the Bidimensional Acculturation Scale to measure the acculturation-related changes in two languages (Only for Hispanic participants), the Addiction Severity Index to measure use of substances, the Block Food screeners to measure nutrient intake, and the Multidimensional Health Locus of Control to measure perceptions of control over health.

The baseline interviews will last approximately 90 minutes and the 6, 12, and 18-month interviews will be shorter (60 minutes) as they will not include the demographic, acculturation and mental health and health history sections. All interviews will be administered by trained research assistants

supervised by the Project Director, [name] and the study PI. The structured interviews will be administered in English or Spanish, depending on participants' language preferences.

Focus Group

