Based on supportive housing agency data, we expect that our study sample will be 70% male and 30% female. The average age of potential participants across the study sites is approximately 50 years old. Approximately, 85% of participants are 18-65 years old and the rest (15%) are older than 65 years old. Approximately, 57% of participants are expected to be African-American, 28% Hispanic, 9% non- Latino whites Caucasian, and 6% other racial identities. All will have a diagnosed SMI.

Inclusion Criteria

Eligible clients are: active supportive housing agency clients who are residing in supportive housing, are 18 years of age or older (18 to 90 years old), of any race/ethnicity, speak English or Spanish, have chart diagnoses of serious mental illness (e. g., schizophrenia, schizoaffective disorder, bipolar disorder, major depression), and have a BMI > 25, and willing to get a medical clearance letter from a primary care doctor with assistance from the study staff if randomized to the Peer GLB group. Additionally, participants who are randomly assigned to the Peer GLB intervention will have to have been cleared by their primary care physician to participate in light-to-moderate physical activity. Study staff and the staff at the study site (e.g., peer specialists, case managers) will assist participants in getting this medical clearance letter.

Exclusion Criteria

We will exclude clients who are in need of detoxification, are at acute risk of suicide or homicide, fail a capacity-to consent questionnaire, and self-report contraindications to participating in a weight

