"Thank you for your interest in our study. The purpose of this project is to evaluate a free group-based healthy lifestyle program to help [Agency] clients who are overweight or obese reduce and manage their weight. The goal of this program is help participants improve their eating habits and increase their engagement in physical activities. The study is being conducted through a partnership between [Agency] and the Columbia University School of Social Work. If you are eligible and you choose to participate, you will be randomly assigned to either 1) continue receiving your usual services or 2) to continue receiving your usual services plus participate in a 12-months healthy

lifestyle program that will be held at [site]. Random assignment is like a lottery and means that you have a 50/50 chance of being assigned to either group. If you are not randomly assigned to receive the healthy lifestyle program, you will continue receiving your usual services, but you will not participate in the healthy lifestyle program. If you are randomly assigned to receive the healthy lifestyle program, you will continue receiving your usual services and you will also be asked to attend the healthy lifestyle groups every week for 12 consecutive weeks. After you attend the program for 12 weeks, you will be asked to attend follow-up groups once a month for 9 months. Each group will last approximately 90 minutes and will be facilitated by a trained peer specialist.

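### The early discontinuation rule takes people out of the study rather than only out of Peer GLB, and names a Peer GLB-only role to apply it, so loss of 12- and 18-month weights may be somewhat unequal between arms

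*Combined protocol and SAP*

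**What the plan says.** **Leaving the study.** Section 3, Criteria for Early Discontinuation, opens: "Early discontinuation from the study will be ascertained by the group facilitator". The sentence goes on to require consultation with the participant's service providers, such as case managers. The rule covers "participants that develop contraindications to participating in a weight loss program", with active cancer treatment, liver failure and a cardiovascular event as examples, and ends with those who become pregnant or "are planning a pregnancy during the study period will be discontinued from the study". Need of detoxification and acute risk of suicide or homicide are further triggers. Section 12, item 2, also removes participants who become suicidal from the study.

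**Stopping or not starting Peer GLB.** Sections 3 and 7 say that a missing physician letter keeps the person out of the intervention. Section 11 says that after an injury, sudden weight loss, or signs of low blood sugar or low blood pressure, the intervention is stopped on the physician's advice. None of these ends study participation.

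**Follow-up.** The recruitment script in section 7 tells candidates that interviews are wanted from them whichever group they are assigned to. It does not mention people who are later discontinued.

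**Who sees whom.** "Peer GLB will be facilitated by trained peer-specialists employed at the supportive housing agencies" (Description of Peer Specialists). The script tells people assigned to usual care that "you will continue receiving your usual services, but you will not participate in the healthy lifestyle program".

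**Analysis.** Section 2 names logistic regression and generalised linear mixed models. The supplied text states no analysis population and no rule for missing weights. Part of section 12 and the attached grant application were not available for this review.

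**The concern.** The primary outcome is the proportion with 5% weight loss at 12 and 18 months. Cancer treatment, liver failure and pregnancy can each move weight by themselves. Removing people for these reasons after randomisation makes missingness related to the outcome. If the conditions come to light more often in one arm, the same kind of person is dropped there and counted in the other.

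The rule gives the first step of ascertainment to someone who works only with Peer GLB participants, and it names no counterpart in usual care. The direction of any bias depends on the mix of conditions. Dropping illness-related weight loss from Peer GLB works against Peer GLB; dropping pregnancies works in its favour.

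The sections also conflict. One site could stop Peer GLB and keep weighing the person, while another ends all contact, and both would be following the protocol.

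**Working it through.** **1. Inputs from the documents.** 150 per arm (section 1); primary outcome at 12 and 18 months (section 2); follow-up interviews at 6, 12 and 18 months in both arms; $25 per interview (section 7). Scheduled sessions with the facilitator: section 2 implies 12–13 weekly + 6 twice-monthly + 6 monthly = 24–25; the recruitment script implies 12 + 9 = 21; usual care has none. This counts contact, not detection. The plan gives no alpha, power, response rates, dropout or rate of the listed conditions, so it has no figure to reproduce. All rates below are assumptions.

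**2. Scale.** With 150 per arm and a two-sided 5% test of two proportions (pooled null variance), the difference detectable with 80% power is 11.8, 13.3 or 14.3 points at usual-care response rates of 10%, 15% or 20%.

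**3. Bias with no true effect.** Let e be the share with a listed condition, d the fraction of them removed in an arm, p0 the response rate of everyone else and pn the response rate of those affected. The observed rate in an arm is

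[(1 − e)·p0 + e·(1 − d)·pn] / (1 − e·d), with n = 150·(1 − e·d).

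Take p0 = 20% and d = 1 in Peer GLB, so Peer GLB always shows 20%. Example with e = 5%, pn = 50% and none removed in usual care: usual care shows 0.95 × 0.20 + 0.05 × 0.50 = 21.5%, and the bias is −1.5 points.

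| pn | Removed in usual care | Bias in points, e = 2% / 5% / 10% | Rejection rate of a nominal 5% test |
|---|---|---|---|
| 50% | none | −0.6 / −1.5 / −3.0 | 5.2% / 6.1% / 9.3% |
| 50% | half | −0.3 / −0.8 / −1.6 | 5.1% / 5.3% / 6.2% |
| 5% | none | +0.3 / +0.75 / +1.5 | 5.1% / 5.3% / 6.2% |
| 5% | half | +0.15 / +0.4 / +0.8 | 5.0% / 5.1% / 5.3% |
| 20% | none or half | 0 | 5% |
| any | all | 0 | 5% |

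Service providers reach usual care too, so the half-detected rows at 2–5% are the more plausible: 0.8 points or less in either direction.

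**4. Outside this range.** Removing 20% in Peer GLB against 5% in usual care, with a 25% response rate overall and no responders among those removed, gives 0.25/0.80 − 0.25/0.95 = +4.9 points. Nothing in the documents suggests that these conditions would remove so many.

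**5. Power cost of keeping these people.** Take a usual-care rate of 15% and a 13.3-point effect in people without a listed condition (80% power), with none in those affected. At e = 2% / 5% / 10%, power is 77.6% / 73.9% / 67.4% if half of those affected respond in both arms, and 78.8% / 77.0% / 73.7% if 5% do. Removing them equally from both arms gives about 79% / 78% / 76%.

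**The case against.** **Others besides the facilitator see both arms.** The rule requires consultation with service providers, who serve everyone, and its removal sentences are not limited to one arm. BASIS-24 is given at every assessment, and adverse events can be reported by agency staff for any participant. Case managers may well learn of chemotherapy, a heart attack or a pregnancy. This stands: the imbalance is partial, and it concerns the medical contraindications more than suicidality.

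**Usual care is still asked about health.** A reader might infer from section 5, which says of the follow-up interviews that "they will not include the demographic, acculturation and mental health and health history sections", that usual care gets no health questions after baseline. That goes too far. Service use is listed separately from the omitted sections, SF-12 and the Addiction Severity Index remain, and the script describes questions on health and service use.

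**Medical clearance.** Entry relies on candidates who "self-report contraindications to participating in a weight loss program", while "participants who are randomly assigned to the Peer GLB intervention will have to have been cleared by their primary care physician" (section 6). A reader might infer that the physician check removes people from one arm's outcome data. The text does not support this. A missing letter bars only Peer GLB, and the discontinuation rule concerns contraindications that people develop, not those already present at entry.

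**Loose wording.** The word study may have been meant as program, in which case no weights are lost. That is possible, but the section says study more than once, and section 12 does too.

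**Size and choice of target.** The calculation drops affected people entirely, whereas a mixed model could use their earlier visits. Keeping them costs more power than removing them equally. Both points are fair. But equal removal needs truly equal detection after randomisation, which the current rule does not provide.

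**Conclusion.** The point holds as a modest defect that is cheap to correct. The protocol removes randomised participants from the study for reasons related to weight, names a role found in one arm only to ascertain this, and conflicts with the sections that stop only the intervention. Loss of 12- and 18-month weights may therefore be somewhat unequal between arms.

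The size and direction cannot be known from the documents. Under the assumed rates the bias is about 1 point or less in plausible cases. It reaches 3 points only if 10% are affected, half of them respond, and all are found in Peer GLB and none in usual care. It is zero if detection is equal or if those affected respond like everyone else.

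The documents do not support a claim that data will be lost mainly from Peer GLB, or that medical clearance causes the loss. Statements about absent rules cover the supplied text only.

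**What to change.** 1. Reconcile Criteria for Early Discontinuation and section 12, item 2, with the clearance text in sections 3 and 7, the stopping text in section 11 and the recruitment script, so that stopping Peer GLB is separate from leaving the study. Which conditions stop Peer GLB is left as written.
2. State that the 6-, 12- and 18-month outcome assessments continue to be requested in both arms unless the person withdraws consent or the treating team advises against them.
3. Where discontinuation from the study is kept, have it ascertained by a role common to both arms, such as the research assistant with the service providers, rather than by the facilitator.
4. State that everyone is analysed in the arm to which they were randomised.
5. Report discontinuations, with reasons, by arm.

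**Cost.** Wording in a few sections, plus some paid interviews. If 5% of 300 people are retained, that is 15 people, at most 15 × 3 = 45 interviews, and 45 × $25 = $1,125 plus travel. At 2% it is $450 and at 10% $2,250. At 5%, power falls from 80% to about 74–77% under the assumed rates, against about 78% if these people were removed equally from both arms. No added health questions and no change to the clearance requirement are needed.
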